Using a dismantling design to test these possibilities, we propose to recruit 350 patients to obtain a final sample of 300 cases with baseline and follow-up data who are randomized to one of three study groups: 1) six sessions of CBT for anxiety reduction (CBT-AR); 2) six sessions of CBT for anxiety-alcohol de-coupling (CBT-DC); or, 3) the original CBT from the parent R01 with three sessions devoted to anxiety reduction and to anxiety-alcohol de-coupling each (CBT-O). To enhance feasibility of the renewal work and ensure its continuity/interpretability with the parent R01, the population and procedures of the proposed work are matched to those used in the parent R01. In brief, alcohol dependent individuals with a co-occurring anxiety disorder will be enrolled within one week of beginning the 28-day residential AUD treatment program, "Lodging Plus." Patients will undergo five significant assessments: 1) Baseline Assessment (after being deemed eligible but prior to randomization); 2) Post-Treatment Assessment (immediately following the conclusion of the six-session treatment and prior to being discharged from Lodging Plus); 3) One-Month Assessment (about 30 days following completion of the study treatment); 4) Four-Month Assessment (about 120 days following completion of the study treatment); and, 5) Eight-Month Assessment (240 days following completion of the study treatment). Primary alcohol outcomes measures will include categorical variables (any alcohol use) and percent or count variables (e.g., days drinking, drinks per drinking occasion). We will also measure alcohol dependence and hazardous drinking statuses at

Dismantling the Components and Dosing of CBT for Co-Occurring Disorders

follow-ups as well as obtain information about other anxiety or alcohol treatments obtained following the study treatment.

PROJECT DESIGN

Design Overview

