4.3. Parent R01: Studies and Results

4.3.1. Recruitment. Over the four-year recruitment period for the RCT (Aim 2), we enrolled and randomized 344 cases. This works out to 86 randomized cases per year. In the final year of recruitment for the randomized study, we recruited 88 cases. In the no-cost extension period, we recruited 115 AUD TAU only cases. Based on this, we estimate we can typically recruit about 2 cases per week in the proposed work.

4.3.2. Retention. Over the life of the study, our retention rate was 78.5% (i.e., attrition was 21.5%) at the four-month follow-up. Our retention procedures improved significantly as indicated by an 87% retention rate in the final year (i.e., attrition about 13%). Based on this, we estimate a 75% retention rate in the proposed work.

[figure not shown]

4.3.2. Findings. As can be seen in the graphs, the alcohol outcomes obtained in the CBT group were superior to the other groups in all cases. The effects between the randomized groups (CBT vs. PMRT) were small for categorical outcomes (any drinking: $X^2 = 4.05$, $p = .04$, $d = .26$; and any three consecutive days drinking: $X^2 = 3.71$, $p = .05$, $d = .25$) and medium for count outcomes (drinks per month: $X^2 = 25.63$, $p < .001$, $d = .68$; drinking days per month ($X^2 = 10.23$, $p = .001$, $d = .42$; and number of binge days per month: $X^2 = 13.46$, $p < .001$, $d = .48$

[the latter is not shown in the graph]). These results support the key study hypothesis from Aim 2 of

the parent R01; i.e., that CBT would produce superior alcohol outcomes relative to a randomized active treatment control. They further demonstrate that the active treatment control, PMRT, did not significantly improve alcohol outcomes relative to TAU controls; however, since the TAU group was not randomized, caution must be taken when interpreting the latter findings. Although patient's "principal" anxiety disorder did not moderate these study results, level of BL anxiety was the only significant moderator; i.e., lower BL anxiety was associated with reduced CBT effects.

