6.0 STUDY PROCEDURES

6.1. Recruitment Strategy. Strategy: We will recruit individuals entering residential treatment for an alcohol use disorder at the Fairview Hospital Chemical Dependency program (Lodging Plus) for adults in Minneapolis. Participants will be recruited from the Consortium of Addiction Research (CAR) combined screening process, approved as IRB protocol #STUDY00005170. Complete details of the screening process can be found in the protocol for that study. Those who are eligible based on the CAR screening protocol will be invited to participate via the “1404S49427 Invite” and given a copy of the consent form. At the Baseline appointment they will have time to read the consent form and have their questions answered. In addition, they will watch a brief video of the study PI describing key elements of the study. If the staff person conducting the screening appointment is convinced the individual understands the consent form based on their answers to questions highlighting the key elements of participation, the individual will be offered the opportunity to sign the consent form. After signing the Consent Form, the baseline appointment will be completed and the appointments for the CBT therapy will be arranged.

Lodging Plus evaluates approximately 1000 chemically dependent patients per year, approximately 70% of whom are seeking treatment for alcohol dependence. Based on our experience in the parent R01 (see above), we should be able to recruit about two patients per week and a total of about 90-100 patients per year. Based on this, the target sample of 350 will be recruited in slightly less than 4 years. Our attrition rate over the entire life of the study was about 20% but was approximately 15% in the final year. (Note improvements in recruitment and retention over the course of the parent R01 reflects refined and improved methods based on our accumulating experience.) Based on the attrition estimate of 15%, we would have approximately 300 cases with four-month follow-up data, which will well power the study (see power estimates below).

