7.5. Primary Aim: To compare the CBT-DC and CBT-AR groups on alcohol outcomes

We predict that the CBT-DC group will have superior alcohol outcomes compared to the CBT-AR group. The primary intention to treat (ITT) population will include all patients randomized. The per-protocol (PP) population will include patients who completed at least four of six (66%) of the therapy sessions with CBT-O patients not missing any more than one of the three AR or DC content sessions. Hypotheses based on the vicious cycle model and parent R01 findings suggest that without alcohol-anxiety de-coupling therapy, drinking relapse is more likely to occur and more severe when it does occur. Therefore, we consider as primary outcomes both categorical relapse status (yes vs. no) and continuously measurement of relapse severity (percent/number days drinking and drinks per drinking day). Secondary alcohol outcomes tested include categorical status on: a) alcohol dependence (yes vs. no) and hazardous drinking (yes vs. no). Follow-up assessments occur 1-, 4- and 8-months following the conclusion of the study therapy and are keyed to the time since the last assessment. To align study findings with the parent R01, the primary assessment point will be the 4-month FU. However, hypotheses will also be tested across all time points to establish temporal patterns of group effects. We test the hypotheses using mixed effects models if data residuals are

normally distributed and generalized estimating equations (GEE) if the data are non-normally distributed (Gueorguieva, & Krystal, 2004; Liang & Zeger, 1986). Both are flexible regression methods for incomplete repeated measures data and allow continuous and categorical covariates, fixed and time-dependent covariates, and a specification of unstructured as well as structured covariance matrix. Categorical outcomes will be evaluated using chi-square tests of proportions and logistic regression, with statistical significance criterion also set at $p < 0.05$. Zero-inflated negative binomial analyses will be used to contrast the study groups on count variables if warranted by a high percentage of zero alcohol use days over the follow-up (e.g., Agresti, 2002).

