The principal power estimate focuses on categorical analyses since these will provide the most conservative power estimates and because we have somewhat more information available to estimate these outcomes for the Primary Aim study groups. (ES for continuous/count alcohol outcomes all demonstrated larger group effects than the categorical outcomes in the parent R01 [Kushner et al. 2013-a].) The best estimate for the categorical CBT-AR alcohol outcome comes from the PMRT group (also devoted exclusively to anxiety reduction) in the parent R01 (i.e., 53% relapse at four months). The parent R01 does not provide a point estimate for the CBT-DC group relapse rate but our prediction that the CBT-DC group will ameliorate all (or most) of the deleterious effect on recovery conferred by a co-occurring anxiety disorder allows us to place this estimate at 21%; i.e., the relapse rate at four months of an AUD treatment group with no co-occurring anxiety disorder (Kushner et al., 2005; also see Driessen et al., 2001 for similar estimates). These estimated results would represent a large effect size ($OR = 4.2$), which would require a sample of only 41 per group to identify an effect at an $\alpha = .05$ level with 80% power; however, a larger sample size would be required to identify other predicted effects with the same power. Further, we cannot be certain that our empirically- and theoretically-informed prediction that the CBT-DC will mitigate all/most of the risk for relapse conferred by co-occurring anxiety disorder is correct until the study is conducted. Therefore, we also calculated a minimum detectable ES showing that we could detect an OR as small as 2.3 with 80% power in the planned sample size using a two-tailed test and 0.05 alpha-level. Although we would be at a higher risk of missing effects even smaller than this, such negative findings would not constitute a meaningful Type II error because they would be of increasingly trivial clinical importance (e.g., Ferguson, 2009). **Therefore, the Primary Aim will be put to a meaningful and scientifically valid test under a wide range of clinically meaningful effect sizes.**

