7.6. Secondary Aim: To compare the CBT-DC and CBT-O groups on alcohol outcomes

The importance of this comparison includes confirming our hypothesis that 6 DC sessions are superior to 3 DC sessions in terms of alcohol outcomes (DC dose: high vs. low) while also ruling out the alternative hypothesis that, contrary to study predictions, de-coupling therapy elements can only exert a therapeutic effect on alcohol outcomes when combined with anxiety reduction elements ("synergy"). Regarding the affirmative dose prediction, we can estimate the effect of the CBT-O group to be the same as that of the CBT in the parent R01 (i.e., 41% relapse at 4 months), while keeping all other parameters, including the CBT-DC group effect estimate of 21% relapse, the same as outlined for the Primary Aim. These estimated results would represent a medium effect ($OR = 2.6$), which would require a sample of 94 per group to identify with 80% power an effect with $\alpha = 0.05$. (Again, we anticipate continuous/count tests will have greater power than categorical tests.) If, however, contrary to our study predictions, synergy between the therapy components is necessary,

then we would expect CBT-DC to resemble TAU only in outcome (61% relapse) with the CBT-O result still being the same as in the parent R01 (again, 41% relapse). This would provide roughly the same power to detect the unexpected synergy effect as there will be to detect the predicted dose effect; albeit, with opposite directional effects.

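### The plan forecasts 75% retention in section 4.3.2 but sizes the four-month sample on 15% attrition in section 6.1; at 75% it would have about 262 cases (87 per group), not 300, and fewer than the 94 per group stated for the Secondary Aim.

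*Combined protocol and SAP*

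**What the plan says.** Section 4.3.2 (Retention) reports the parent study's experience: "Over the life of the study, our retention rate was 78.5% (i.e., attrition was 21.5%) at the four-month follow-up". It adds that retention in the final year was 87%, and then forecasts for this trial: "Based on this, we estimate a 75% retention rate in the proposed work". No time point is attached to the 75%.

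Section 6.1 describes the same parent study in rounder terms: "Our attrition rate over the entire life of the study was about 20% but was approximately 15% in the final year". It carries the more favourable of these forward: "Based on the attrition estimate of 15%, we would have approximately 300 cases with four-month follow-up data".

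The resulting target also appears in the Abstract, the Design Overview and the Schema, each of which plans to "recruit 350 patients to obtain a final sample of 300 cases with baseline and follow-up data".

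Section 7.5 says that "the primary assessment point will be the 4-month FU", and its power paragraph says "we could detect an OR as small as 2.3 with 80% power in the planned sample size". Section 7.6 assumes 41% versus 21% relapse for the Secondary Aim, "which would require a sample of 94 per group to identify with 80% power", and says a synergy effect in the opposite direction (61% versus 41%) would be detected with roughly equal power. Section 7.7 repeats the 94 per group for the Tertiary Aim.

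**The concern.** Both sentences forecast retention in this trial, and both are current text. One implies 25% attrition and the other 15%. The 75% is presented as following from parent rates of 78.5% and 87%, yet it is lower than either. It could be a slip or a deliberately cautious figure, and the documents do not say which.

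The primary outcomes are assessed at four months, so four-month retention fixes the number of analysable cases. Three stated figures depend on it: the final sample of 300, whether 94 per group is reached for the Secondary Aim, and the minimum detectable odds ratio for the Primary Aim. A reader cannot tell which retention rate governs them.

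**Working it through.** **Inputs.** Recruited: 350, in three groups. Equal allocation is an assumption, supported by the 100 per group in section 7.8. Retention: 75%, 78.5% and 87% (section 4.3.2); 80% and 85%, from attrition of about 20% and 15% (section 6.1). Relapse rates: 53% versus 21% (section 7.5); 41% versus 21% and 61% versus 41% (section 7.6). Two-sided alpha 0.05, power 80%.

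**Step 1: the plan's own 300.** 350 × 0.85 = 297.5, or 99.2 per group. The stated figure of about 300 follows from 15% attrition.

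**Step 2: the other rates.**

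| Four-month retention | Source | Cases | Per group |
|---|---|---|---|
| 75% | 4.3.2, forecast for this trial | 262.5 | 87.5 |
| 78.5% | 4.3.2, parent, whole study | 274.75 | 91.6 |
| 80% | 6.1, parent, whole study, rounded | 280 | 93.3 |
| 85% | 6.1, parent, final year | 297.5 | 99.2 |
| 87% | 4.3.2, parent, final year | 304.5 | 101.5 |

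Only the final-year rates give about 300. Reaching 94 per group needs 94 × 3 / 350 = 80.6% retention.

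**Step 3: the plan's 94 per group.** The usual two-proportion formula, with p̄ the mean of p1 and p2, is

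n = [1.96 √(2p̄(1−p̄)) + 0.842 √(p1(1−p1) + p2(1−p2))]² / (p1−p2)².

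For 41% versus 21%, p̄ = 0.31 and n = (1.282 + 0.537)² / 0.20² = 82.8, so 83 per group. The continuity-corrected version is (n/4)[1 + √(1 + 4/(n|p1−p2|))]² = 92.5, so 93, close to the stated 94. For 53% versus 21% the corrected formula gives 41, which matches section 7.5. The plan's figures therefore look continuity-corrected.

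**Step 4: power at the smaller sample.**

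Power = Φ{[|p1−p2| − c − 1.96 √(2p̄(1−p̄)/n)] / √[(p1(1−p1) + p2(1−p2))/n]},

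with c = 1/n if corrected and 0 if not. For 41% versus 21% at n = 87, corrected: (0.200 − 0.0115 − 0.1374) / 0.0685 = 0.746, and Φ(0.746) = 0.772. Each cell below is corrected / uncorrected.

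| Comparison | n = 87 | n = 92 | n = 100 |
|---|---|---|---|
| Secondary Aim, 41% vs 21% | 0.772 / 0.820 | 0.798 / 0.841 | 0.833 / 0.870 |
| Synergy, 61% vs 41% | 0.705 / 0.756 | – | 0.771 / 0.812 |
| Primary Aim, 53% vs 21% | 0.992 / 0.995 | – | 0.997 / 0.998 |

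**Step 5: minimum detectable odds ratio.** Solving the same expression for the lower rate that gives 80% power against 53%, corrected / uncorrected: 2.34 / 2.24 at 100 per group, 2.44 / 2.32 at 92, and 2.51 / 2.38 at 87. The stated 2.3 fits about 100 per group.

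**The case against.** The strongest reply is that the two rates need not describe the same time point. The 15% is explicitly a four-month figure. The 75% is for the proposed work as a whole, which was planned to run to eight months, and 75% at eight months could sit alongside 85% at four. That would also explain why it is below both parent rates. But no text supports this reading, and the sentence draws on a rate given at four months. If it is what was meant, stating the time point settles the matter.

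It can also be said that the 75% is one sentence in the preliminary-studies section, that no calculation uses it, and that the rest of the chain (350, 15%, 300, 100 per group) agrees with itself. That is true, and it makes a slip plausible, but it does not tell the reader which rate to rely on.

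The points about size largely stand:

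- Section 7.5 plans chi-square tests and mentions no continuity correction. Uncorrected, the Secondary Aim requirement is 83 per group, which 75% retention still meets with power 0.82.
- At 78.5% or 80% retention the gap to 94 is one to two patients per group, close to rounding.
- Under the corrected formula, synergy power is already below 80% at 100 per group (0.77). Attrition lowers it further but does not create that shortfall.
- Section 7.5 notes that the count outcomes showed larger effects in the parent study, and section 7.6 expects them to have more power.

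**Conclusion.** The concern holds: the plan is wrong as written. It forecasts two retention rates for this trial without reconciling them, and the lower one does not deliver its stated sample.

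At 75% the expected four-month sample is about 262, some 38 short of 300, and 87 per group is 7 short of the stated 94. Secondary Aim power falls by 0.05 to 0.06, and goes below 80% only under the corrected formula. Synergy power is below 80% under both formulas at 87 per group. The detectable odds ratio of 2.3 becomes about 2.4 to 2.5. The Primary Aim at its planned effect is unaffected.

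These figures assume equal allocation, that the 75% applies at four months, and the relapse rates in sections 7.5 and 7.6. The 0.40 SD mechanism check in section 7.8 is not affected, because it uses the immediate post-treatment assessment, for which no retention rate is given.

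**What to change.** Choose one four-month retention figure, state its time point, and use it throughout.

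- **If 75% stands at four months:** replace 300 with about 262 (87 per group) in the Abstract, Design Overview, Schema and section 6.1. Restate the Secondary Aim power, the synergy power and the minimum detectable odds ratio (about 2.4 to 2.5), naming the formula used.
- **If 85% stands:** correct the sentence in section 4.3.2 and show the parent's whole-study rate of 78.5% as a sensitivity case (275 cases, 92 per group, Secondary Aim power 0.80 to 0.84).
- **If 75% was meant for a later time point:** say so in section 4.3.2, and treat the four-month rate as in the 85% case.

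Do not restate the section 7.8 mechanism check from four-month attrition. The cost is a change of wording and a few restated figures, with slightly less favourable stated power if 75% is kept. Enrolment does not change.

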4.4. Parent R01: Significance

The practical significance of the parent R01 findings is in showing that augmenting AUD TAU with a six-session CBT reduces four-month relapse rates in those with co-occurring anxiety disorders by about one-quarter to one-third (i.e., TAU = 60%; PMRT = 53%; CBT = 41%). Although this eliminates only about half of the estimated increase in relapse risk attributable directly to the presence of a co-occurring anxiety disorder (e.g., Kushner et al., 2005), the large number of AUD treatment patients affected by co-occurring anxiety disorders (up to 50% of all cases) amplifies the potential benefit to the public health of these results. The aspects of the parent R01 findings with the greatest potential for theoretical significance are those pointing to the active ingredients by which the CBT improved AUD outcomes. The CBT and PMRT both produced a significant reduction in the percent of patients experiencing clinical-level anxiety at the post-treatment assessment, while only

the CBT demonstrated significantly better alcohol outcomes relative to TAU at the four-month assessment. These findings reinforce past studies showing that anxiety disorder treatment does not produce detectable improvements in alcohol outcomes (above). More importantly, these findings imply that the de-coupling therapy elements were the active ingredients that improved alcohol outcomes in the CBT group. This conclusion has the theoretical potential of informing modification to the CBT that would substantially improve its clinical effectiveness.

4.5. Parent R01: Plans

The parent R01, while having successfully achieved its specific aims and confirmed its primary hypothesis, fell short of producing a clinical "breakthrough" defined as a treatment with large clinical effects that eliminates most or all of the deleterious effect of co-occurring anxiety disorders on AUD treatment outcomes. Fortunately, the results of the parent R01 point the way to modifications to the CBT that could further amplify its therapeutic effects. Our plan is to employ a "dismantling" research approach in a renewal of the parent R01 to implement and test these ideas. We believe this will allow us to achieve our ultimate goal of establishing a brief CBT intervention that can fully (or largely) mitigate the deleterious effect of common co-occurring anxiety disorders on AUD treatment outcomes.

5.0 RESEARCH DESIGN

5.1 . Overview.

This is a between-group randomized clinical trial with 350 patients to randomized to one of three study groups: 1) six sessions of CBT for anxiety reduction (CBT-AR); 2) six sessions of CBT for anxiety-alcohol de-coupling (CBT-DC); or, 3) the original CBT from the parent R01 with three sessions devoted to anxiety reduction and three sessions devoted to anxiety-alcohol de-coupling (CBT-O). Alcohol dependent individuals with co-occurring SAD, GAD or PD/Ag will be enrolled within one week of beginning the 28-day residential AUD treatment program, Fairview "Lodging Plus" in Minneapolis. All study treatments will take place while patients are still in the Lodging Plus program; i.e., one hour sessions during patient free-time (i.e., no conflicting programming) for six consecutive business days. Patients will undergo four significant assessments: 1) baseline (after being deemed eligible but prior to randomization); 2) post-treatment (immediately following conclusion of the six-session treatment and prior to being discharged from Lodging Plus; 3) one-month (30 days following completion of the

study treatment); and, 4) four-months (120 days following completion of the study treatment); 5)) Eight-Month Follow-Up Assessment (240 days following completion of the study treatment). Primary relapse measures will include categorical (any alcohol use, hazardous drinking, alcohol dependence) and continuous/counts (e.g., days drinking, drinks per drinking occasion, binge days) variables. Following approval of MOD00013885 we will not complete the eight-month follow-up assessment on recruited participants. Because the primary outcomes for this study will be collected at the four-month follow-up appointment, this modification will allow us to continue recruitment through February 2020, with recruited participants able to complete the four-month follow-up prior to the end of the funding period for this project in June 2020.

